#### 9. Quantitative Analytic Plan:

Aim 1: To compare between the intervention versus usual care arms in the change from baseline in KCCQ (Primary outcome) and EQ5D (secondary outcome) at 90 and 180 days. The analysis will be performed from an intention to treat principle. First, descriptive statistics (mean, standard deviation, median, inter-quartile range, and frequency distribution) will be calculated to summarize, at baseline, patients' demographic and comorbidities including previous hospitalizations, cardiac history (heart function and coronary disease), medical and health service utilization information (including medication possession ratio, HF self-care index, BNP levels, enrollment into HF clinics / programs, visits with primary care and cardiologists), and the primary outcome of interest (KCCQ, overall score) according to randomized arms. Log-transformation of variables and outcomes of interest will be performed to approximate normality when appropriate. Linear mixed-effects (LME) model will be utilized for the analysis of this aim, where the response variable is KCCQ, fixed effects include treatment group, time (0 = baseline, 1 = at 90 days, 2 = 180 days), treatment group by time interaction, and other important demographic variables identified in the descriptive analysis, and random effects include site-specific random intercept, subject-specific random intercept (nested within site) and subject-specific random slope of time. This modeling approach has been shown to provide an unbiased and efficient estimate of the longitudinal treatment effect in a variety of situations, such as in the presence of missing data, imbalance of the primary outcome at baseline, and covariance heterogeneity between treatment groups. In this way, we could compare the intervention effects at 90 days and whether residual effects exist at 180 days. The random site effect is used to model the clustering effect of patients in the same study site and random subject effects are used to model the variability in the subject-specific trajectory and the correlation of repeated measures within subject. Residual analysis will be conducted to examine the appropriateness of the functional forms of each fixed effect, and Information criteria (AIC, BIC) will be used to choose the correlation structure.

Secondary: Same modeling technique will be used to study EQ5D as the outcome instead of KCCQ.

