Aim 2: To compare between the intervention versus usual care arms in hospitalization or death at 90 and 180 days after the randomization. For this analysis Cox proportional hazards model will be utilized where the event is a composite outcome that represents either hospitalization or death. Any patient who does not experience the event by 180 days will be denoted as censored. The main exposure is treatment group and other covariates include patient demographic and comorbidity information as described above. We will examine the differences in outcome at both 90 and 180 days. The appropriateness of the proportional hazards assumption will be examined and any violation of the assumption will be addressed. The appropriateness of the functional forms of each covariate will be assessed through residual analysis.

Aim 3: To compare between the intervention versus usual care arms in the change from baseline in patient's (a) HF Self Care index and (b) BNP levels, we will use the same linear mixed-effects modeling approach as described in Aim 1.

Subgroup and Sensitivity Analyses: In order to understand potential heterogeneity of treatment effects, stratified analyses will be conducted by our randomization stratifiers such as co-interventions or not, ejection fraction ( $\geq 40\%$  &  $< 40\%$ ), and hospitalizations in the previous 6 months ( $> 2$  &  $\leq 2$ ). Given that baseline KCCQ scores, HF self-care behavior, comorbidity burden, depression symptoms and caregiver support could potentially change the outcome of HF, we will conduct test for multiplicative interaction between the condition of interest (e.g. depression with PHQ-8  $\geq 10$  vs.  $< 10$ ) and the study arm allocation (intervention vs. usual care arm) on the patient outcomes of interest described in Aims 1 and 2. *If any these interaction terms are significant at an alpha level of 0.05 or less*, subgroup analyses will be conducted (e.g. number of comorbidities below and above the median, baseline KCCQ scores above and below the median, and by presence or absence of significant depression symptoms or caregiver support) depending on the feasibility by sample size. Sensitivity analyses will be performed by study site to determine the impact of setting in our study findings and potential variation of findings.

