Sample Size and Power Considerations: The overall study sample will be 375 (225 patients from Phoenix VAMC and 150 patients from Providence VAMC). Statistical power for the aims 1 and 2 is estimated given these are the most relevant and the most restrictive in terms of power estimations. Under a conservative dropout rate of 15% for 180 days of follow-up for the main outcomes (Aims 1 and 2), we estimate the power with an effective sample size of 316 (15% less than the total sample) and a 2-sided significance level of 0.05 using nQUERY Advisor 7.0®. For aim 1, we assess the power to detect a clinically significant change in KCCQ of 5 points, assuming a baseline score of 63 (our preliminary studies), with a common standard deviation of 15 for the study arms, using a 2-sample t-test. For aim 2, we assess the power to detect a relevant decrease in rehospitalization or death risk of 25-30% at 180 days using a Cox Proportional Hazards model. Based on our preliminary data of 20,000 Veterans with ejection fraction <40% hospitalized with HF, their rehospitalization rates at 6 months is ~40%. Assuming similar event rates for rehospitalization or death, as shown in Table 2, we have good power to detect the proposed outcomes at very conservative estimates of effective sample size (n=158 in each arm, which is 85% of the total proposed recruitment target). Repeated measures at 90 and 180 days are also likely to add to the statistical power in Aim 1 to detect differences at the subgroup levels.

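### The mixed model for KCCQ, EQ-5D, self-care and BNP leaves the baseline mean free in each arm, so it gives up precision that the baseline scores already collected would supply

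*Combined protocol and SAP*

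**What the plan says.** In section 9, Quantitative Analytic Plan, the Aim 1 target is "To compare between the intervention versus usual care arms in the change from baseline in KCCQ (Primary outcome") and EQ-5D at 90 and 180 days. The linear mixed model is one "where the response variable is KCCQ", with baseline as time 0, and its "fixed effects include treatment group, time (0 = baseline, 1 = at 90 days, 2 = 180 days), treatment group by time interaction". The only further fixed effects are "other important demographic variables identified in the descriptive analysis". The "random effects include site-specific random intercept, subject-specific random intercept (nested within site) and subject-specific random slope of time".

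Nothing sets the two arms to a common baseline mean, and baseline KCCQ is not a covariate. It appears only in the descriptive summary and, under Subgroup and Sensitivity Analyses, as a possible effect modifier. The plan does not name the coefficient to be tested.

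The plan says that this approach gives an "unbiased and efficient estimate of the longitudinal treatment effect in a variety of situations", and counts baseline imbalance of the primary outcome among those situations. EQ-5D uses the same technique. For the HF Self-care Index and BNP, "we will use the same linear mixed-effects modeling approach as described in Aim 1". Table 1 shows that all four outcomes are measured at baseline.

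**The concern.** In this model the group term is the difference between arms at baseline, and the group-by-time terms are differences in change from that baseline. Allocation is random and 1:1 (section 5, Randomization and retention), so the expected baseline difference is zero. Estimating it freely adds the noise of the baseline means to the treatment contrast.

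A change-from-baseline contrast also subtracts the whole of any chance baseline imbalance d, when only r × d carries forward on average. That leaves an error of -(1-r)d, given the imbalance.

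A related point concerns the planned covariates. One that is constant over time and enters only as a main effect shifts baseline and follow-up equally. With complete data it drops out of the group-by-time estimate.

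At stake is the width of the confidence intervals for the primary outcome and three others. The plan's own power is 0.84 for 5 points, which it treats as the smallest important change, and 0.76 for 4.5 points.

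**Working it through.** **Inputs from the documents.** 375 patients, 1:1; 15% dropout; 158 per arm after loss; SD 15; difference 5 points; two-sided 0.05; two-sample t-test (Sample Size and Power Considerations). The text gives an "effective sample size of 316 (15% less than the total sample) and a 2-sided significance level of 0.05". It does not say whether SD 15 is that of the score or of the change.

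**Assumed.** The correlation r, because the documents give none. Range shown: 0.4 to 0.9.

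**1. The plan's own figure.** SE = 15 × √(2/158) = 1.688. Power = Φ(5/1.688 - 1.96) = 0.842, against 0.84 in Table 2. The other rows give 0.760, 0.903 and 0.945 against .76, .90 and .95. Table 2 reproduces. It rests on a t-test, so it does not depend on the mixed model's form.

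**2. Complete data.** Per-patient variance, with score SD σ:
- change from baseline: 2σ²(1-r)
- baseline as predictor, or one shared baseline mean: σ²(1-r²)
- ratio: (1-r²) / [2(1-r)] = (1+r)/2

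The reduction is therefore 30%, 25%, 20%, 15%, 10% and 5% for r = 0.4, 0.5, 0.6, 0.7, 0.8 and 0.9.

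**3. With loss to follow-up.** Exact generalised least squares variances for 187.5 per arm, score SD 15, equal correlations between visits, categorical visits, 8% missing at day 90 and 15% at day 180, with and without the treatment main effect:

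| r | Day-180 SE, planned | Day-180 SE, shared baseline | Variance cut | Power for 5 points |
|---|---|---|---|---|
| 0.4 | 1.79 | 1.54 | 27% | 0.80 to 0.90 |
| 0.5 | 1.64 | 1.45 | 22% | 0.86 to 0.93 |
| 0.6 | 1.47 | 1.34 | 18% | 0.92 to 0.96 |
| 0.7 | 1.28 | 1.19 | 13% | 0.97 to 0.99 |
| 0.8 | 1.05 | 1.00 | 9% | above 0.99 for both |
| 0.9 | 0.74 | 0.73 | 4% | above 0.99 for both |

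**4. Other forms of the model.** With time linear as 0/1/2, the same loss pattern gives cuts of 31%, 25%, 20% and 14.5% for r = 0.4 to 0.7. Under four assumed random intercept and slope structures with 15% dropout (baseline to day-180 r of 0.47 to 0.61), the day-180 cut is 12% to 24%. The loss does not depend on how time is coded.

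**5. If SD 15 is the SD of the change.** With 158 per arm, the planned contrast has power 0.84 whatever r is. Multiplying the variance by (1+r)/2 raises it to 0.94, 0.93, 0.91 and 0.89 for r = 0.4 to 0.7, and to 0.88 and 0.86 for r = 0.8 and 0.9.

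**6. Chance imbalance.** One SE of baseline imbalance is 15 × √(2/187.5) = 1.55 points. At r = 0.5 the planned contrast then carries an error of 0.5 × 1.55 = 0.77 points. Over repeated randomisations this averages to zero.

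**The case against.** The planned model is valid. It is unbiased over randomisation, keeps the nominal error rate and uses all available visits. A reader might infer from the conditional error in step 6 that the primary result is biased, or that the stated power is wrong. Neither follows: the error averages to zero, and Table 2 reproduces on its own inputs. If SD 15 is that of the score, the planned contrast still reaches 0.84 or more once r is about 0.5 or higher.

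The size of the gain rests on a correlation that the documents do not give, and at r of 0.8 to 0.9 it is small. That stands, and it is why a range is shown.

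A reader might also infer that the planned covariate adjustment is useless. The cancellation is exact only with complete data and main-effect-only covariates. The plan expects dropout and does not say how covariates enter, so the supportable statement is that they add little precision.

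Nor is the remedy unconditional. The trial is open-label (section 1, Overview). Sections 5 and 8 place randomisation after enrolment and baseline data collection at the enrolment visit, but do not say that the questionnaires and BNP precede knowledge of the arm. That order is likely, but a shared baseline mean relies on it.

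Categorical visits are a separate choice with a price. If time is meant to be linear, at r = 0.5 the planned day-90 SE is 0.82, against 1.40 with categorical visits and a shared baseline. Keeping time linear and sharing the baseline gives 0.71.

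Finally, the plan's efficiency statement is hedged and relies on cited sources not available here. It cannot be called false in general. What can be said is that this form is not the most efficient one for a randomised comparison.

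**Conclusion.** The point holds as a loss of precision. That the planned test is of change from baseline is inferred from the stated aim and the interaction term, since no coefficient is named. With complete data, the treatment-effect variance could be multiplied by (1+r)/2. That is a fall of 15% to 30% if r lies between 0.7 and 0.4, and of 5% to 10% if r is 0.9 to 0.8. With 15% loss and equal correlations, the day-180 fall is 13% to 27% for r of 0.7 to 0.4. A 25% fall is worth about as much as a third more patients (1/0.75 = 1.33).

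These sizes rest on assumed correlations. For Aim 3 the relevant baselines are the self-care and BNP values, whose correlations are also not given, so no figure can be attached to those outcomes. The change is worth making because the baseline data are already collected, but the trial would remain valid without it.

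**What to change.** In section 9, Aim 1:

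- Drop the treatment-group main effect, so that both arms share one baseline mean and the arm-by-time terms carry the treatment effect. Alternatively, model days 90 and 180 only, with the baseline value of the outcome, by visit, as a covariate.
- Name the contrasts to be tested at 90 and 180 days.
- Enter other prespecified baseline covariates with a visit interaction.
- Use the same form for EQ-5D, the HF Self-care Index scales and BNP, each with its own baseline.
- State in sections 5 and 8 that the baseline questionnaires and BNP are obtained before the assignment is known.
- Decide separately whether visit is categorical or linear, and say why. Categorical visits avoid assuming a linear effect but give a wider day-90 interval.

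The cost is plan wording only, with no added patients, visits or measurements. The condition is that baseline measurement does precede knowledge of the arm.

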#### Potential for HF-SMA to promote behavioral change

In addition to disease state monitoring and medication management, HF patients require intense training in self-care, such as weight monitoring and adherence to diet and medications, and early symptom recognition, which is difficult and time-consuming to provide in the traditional one-on-one visit setting. Based on the self-management support and system re-design constructs of the chronic care model, HF-SMA has the potential to address the self-care needs of these patients in a coordinated and efficient manner. The mechanisms at which the self-management support in HF-SMA could lead to behavioral modification can be explained, at least in part by the Social Cognitive Theory (Figure 1). Based on the Social Cognitive Theory, promotion of healthy self-care behaviors in the SMA setting such as sodium restriction, weight-monitoring and medication adherence can be explained by determinants at the personal and environmental levels. At the personal level, the SMA providers will use interactive discussions to shape expectations (anticipatory outcomes of a behavior) in an environment of peer support and use the group dynamic (environmental factor) to promote observational learning (behavioral acquisition that occurs by watching the actions and outcomes of other's behavior which include credible role models). The SMA provider will provide reinforcement for healthy behavior (both direct and vicarious); and will foster self-control (regulation of goal-directed behavior performance, self-monitoring, goal setting, problem solving and self-reward) through self-reinforcement and promotion of self-efficacy, to increase healthy behaviors stated above. In addition, social support is also increased through education of family and support members when present. Our previous studies of SMAs in diabetes have shown positive results in improvement in self-care behaviors and glycemic control.

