**5. Randomization and retention:** Once enrolled, patients will be randomly assigned on a 1:1 ratio to intervention or placebo arms using a stratified block randomization method with block sizes of 4 in each site to ensure balance of the stratified variables. Stratification will be based on the study site and the presence or not of: a) co-intervention (enrollment to HF clinic, support group or education), b) ≤2 hospitalizations in the last 6 months, and c) left ventricular ejection fraction <40%. Randomization will be done by the call-in method to a central computer administered by the study coordinator at Providence VAMC, the coordinating site. To ensure subject safety and continuous engagement in study procedures, patients will be called by phone by study staff on a monthly basis following randomization to answer any questions that may arise, ask for participation in HF programs and doctor's visits, ER visits, document adverse events and maintain study engagement. Patients in the control arm will be invited to participate in HF-SMAs at the end of the study, to honor patient's preferences.

Our preliminary data showed that our recruitment in prior SMA research has been successful, ~50-60% of those screened and eligible agreed to enroll in SMAs; and then about 90% of those enrolled finished the study. Reasons for drop out are: geographic mobility, change in work schedule, incarceration, and homelessness. Yet, we have been able to maintain a good retention rate, through a combination of excellent relationships with participants, and a perceived value of the study to clients.

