**6. HF-SMA:** The HF-SMA team includes a dietitian, a health psychologist, a nurse, and a nurse practitioner and/or a clinical pharmacist; one of which will lead the group discussions. Caregivers if available and willing, are allowed and encouraged to attend SMAs but NOT required, similar to how family members are allowed and encouraged to attend usual care clinic visits, but NOT required. Inadvertent loss of privacy is a concern in SMAs and we will clearly state that risk in the draft informed consent form (Appendix). At the beginning of each session the facilitator will provide SMA group guidelines for participation for the participants, caregivers and providers during the group interaction. Participants will be advised regarding appropriateness in sharing, as well as the expectations of privacy and confidentiality for patients and caregivers. Specifically, patients will not be asked to reveal any sensitive information about themselves and will be advised that the providers will not reveal any of the participants personal information during the group sessions. The SMA providers in both sites are very experienced and have been trained to respect privacy and avoid eliciting sensitive information. The session will start with an assessment of the patients and their needs followed by pre-assigned disease self-management education, followed by patient-initiated disease discussion, and conclude with break-out sessions of individualized behavioral intervention, medication reconciliation and case management by the multi-disciplinary team. The HF-SMA group will consist of 4-6 patients (and caregivers if present), of 2h duration broken down into:

1) **Patient intake** (10 min): they will complete a salt intake survey (appendix), blood pressure, heart rate, weight, leg /sacral edema, heart and lung sounds (nurse, pharmacist, and/or nurse practitioner).

They will also undergo medication reconciliation (10-15 minutes each patient): Clinical pharmacist or nurse practitioner reviews patients' medications against hospital discharge instructions and performs brief medication therapy management evaluation. In order to perform a thorough assessment of medications and adherence, we will ask the patient to bring all the medications in all HF-SMA visits (prescribed and non-

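### The Aim 1 and Aim 3 models have no SMA-group term, so if the SMA effect varies between groups, the interval for the primary outcome will be somewhat too narrow

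*Combined protocol and SAP*

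**What the plan says.** Allocation is by individual patient (item 5, Randomization and retention): "patients will be randomly assigned on a 1:1 ratio to intervention or placebo arms"; the comparator is usual care. Grouping exists only in the intervention arm (item 6, HF-SMA): "The HF-SMA group will consist of 4-6 patients (and caregivers if present), of 2h duration". Usual care (item 7) comes from each patient's own physicians, often with one-to-one heart failure clinic visits. The background section on behavioural change makes the group part of the mechanism, since providers are to "use the group dynamic (environmental factor) to promote observational learning".

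The Aim 1 model for KCCQ (item 9, Quantitative Analytic Plan) has fixed effects for treatment, time (baseline, 90 and 180 days), their interaction and covariates. Its random part reads: "random effects include site-specific random intercept, subject-specific random intercept (nested within site) and subject-specific random slope of time". EQ5D uses the same technique, and for Aim 3 the plan states "we will use the same linear mixed-effects modeling approach as described in Aim 1". The Aim 2 Cox model is described by "The main exposure is treatment group and other covariates include patient demographic and comorbidity information as described above", with no frailty or clustered variance. Aim 1 power in Table 2 was computed "using a 2-sample t-test", with patients taken as independent.

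The documents give no ICC for SMA groups. They do not say whether groups are closed or rolling, and the data collection timeline (Table 1) has no entry for group membership.

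**The concern.** This is a partially nested design: one arm is treated in groups and the other is not. If some groups work better than others, the follow-up scores of patients who shared a group are positively correlated. The variance of the SMA-arm mean is then larger than the planned model allows.

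None of the planned terms absorbs this:
- The site intercept is shared by both arms and largely cancels from the treatment contrast.
- Subject effects are assumed independent between patients.
- Choosing a correlation structure by AIC or BIC follows text about repeated measures within a subject and names no group level.
- Sensitivity analyses by site do not reach groups within a site.

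At stake is the interval for the primary outcome. The error runs one way: any positive within-group correlation makes the planned interval too narrow. If group identity is not recorded, the correction cannot be fitted afterwards and the sponsor cannot show that clustering was negligible.

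**Working it through.** **Inputs from item 9.** 158 patients per arm after 15% dropout, SD 15, difference 5 KCCQ points, two-sided 5% level.

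**The plan's own figure.** SE = 15 × √(2/158) = 1.688. Power = Φ(5/1.688 − 1.96) = Φ(1.003) = 0.842. Table 2 states 0.84, so it reproduces under independence.

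**Assumptions.** ICC at follow-up of 0.01, 0.05 and 0.10, created by shared treatment in the SMA arm.

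**Trial patients per group (m).** Item 4 plans 50 and 75 enrolments a year at the two sites, so 25 and 37.5 SMA patients. Times four sessions, that is 100 and 150 patient-sessions a year with full attendance. Weekly sessions give 100/52 = 1.9 and 150/52 = 2.9 trial patients per session. Sessions every other week give 100/26 = 3.8 and 150/26 = 5.8. The preliminary work describes weekly sessions at Phoenix and clinics that take referred patients, so the 4-6 in a group need not all be trial patients. Hence m = 2-3 is the leading case and 4-6 the upper case.

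**Formulas.** Design effect in the SMA arm: DE = 1 + 0.85 × (m − 1) × ICC, where 0.85 is the share of group-mates retained. True variance of the arm difference relative to that assumed: r = (1 + DE)/2. Actual type I error = 2 × (1 − Φ(1.96/√r)). SE shortfall = 1 − 1/√r.

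Example, m = 3 and ICC 0.10: DE = 1 + 0.85 × 2 × 0.10 = 1.17; r = 1.085; type I error = 2 × (1 − Φ(1.96/1.0416)) = 5.99%; shortfall = 4.0%.

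| ICC (assumed) | m=2 | m=3 | m=4 | m=5 | m=6 |
|---|---|---|---|---|---|
| 0.01 | 5.05% | 5.10% | 5.15% | 5.20% | 5.24% |
| 0.05 | 5.24% | 5.49% | 5.74% | 5.99% | 6.24% |
| 0.10 | 5.49% | 5.99% | 6.49% | 7.00% | 7.51% |

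At ICC 0.10 the planned SE is 2.1-4.0% too small for m = 2-3 and 5.8-9.2% too small for m = 4-6.

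**Simulation check.** 188 SMA patients in groups of m, 187 usual care, 15% random dropout, unadjusted t-test, 40,000 trials per cell. For m = 2 to 6 the rates were 5.3, 5.5, 5.7, 5.9 and 6.2% at ICC 0.05, and 5.5, 6.0, 6.6, 7.0 and 7.5% at ICC 0.10.

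**Using the baseline.** The t-test is not the planned model. With an assumed baseline-to-follow-up correlation of 0.5, residual variance falls by the factor 1 − 0.5² = 0.75, so the group share becomes ICC/0.75. The same formula then gives 5.3-5.7% and 5.7-6.3% (m = 2-3) and 6.0-6.7% and 7.0-8.4% (m = 4-6) at ICC 0.05 and 0.10. The direction is the same and the size slightly larger.

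**Which correlation counts.** With 32 calendar cohorts of 10, an effect shared by both arms and ICC 0.10, the rejection rate was 5.0% with simple allocation and 3.9% when balanced within cohort. Calendar or scheduling effects common to both arms therefore do not inflate the test.

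**Which group term works.** The tested quantity is the treatment-by-time contrast, a difference in changes from baseline. A group effect that is constant over time cancels from that change. A simulation of the planned model (complete data, 160 per arm, groups of 5, ICC 0.10 at follow-up only, baseline correlation 0.5, 600 runs) gave these mean SEs at 180 days: 1.69 as planned, 1.69 with a group intercept and 1.84 with a post-baseline group effect. Rejection rates were 7.5%, 7.5% and 6.0%, with Monte Carlo error of about 1 point.

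**The case against.** The strongest objection is that inflation requires a particular null. If SMA changes nobody's outcome, shared treatment creates no correlation and the error rate is exactly 5%. Excess rejection needs a zero average effect, with some groups helped and others harmed. With SD 15, ICC 0.10 means a between-group SD of 15 × √0.10 = 4.7 points, so about 15% of groups would be harmed by more than 5 points (Φ(−5/4.7)). At ICC 0.05 the SD is 3.4 points and the share about 7%. This stands: the point is chiefly about interval width when the effect varies between groups.

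Second, the design limits such variation. Sessions follow a fixed four-theme curriculum, and one session per site per month is observed for fidelity for 24 months. Group education and guided discussion take 30-60 minutes of two hours, and much of the rest is individual. Sessions end at about 8 weeks, and item 11 expects effects to fade afterwards. This also stands and points to the lower end of the range at 180 days, though less so at 90 days.

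Three stronger readings are tempting, but the documents do not support them:
- **Leader-level clustering.** Item 6 says of the team members "one of which will lead the group discussions", and clusters formed by leader would be larger. The documents do not give the number of leaders or patients per leader, so no figure can be attached.
- **An underpowered trial.** On the baseline-adjusted approximation, power for 5 points after allowing for groups is 0.86-0.92 at ICC 0.05-0.10, above the stated 0.84. The plan also expects repeated measures to add power.
- **A quantified error for Aims 2 and 3.** Nothing in the documents allows one.

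**Conclusion.** The point holds in a limited form. The plan treats one arm in groups, relies on the group as a mechanism, and analyses the data as if group-mates were independent. If the SMA effect varies between groups, the interval for the primary outcome is too narrow and a test of a zero average effect rejects more than 5% of the time. In the leading case of 2-3 trial patients per group, the excess is at most about 1 percentage point, even at the high ICC of 0.10. With 4-6 it reaches about 2.5 points on the t-test basis.

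Every figure rests on an assumed ICC, on SD 15 and 158 per arm from the plan, and on group sizes inferred from planned recruitment with full attendance. A reader should not infer that the error rate is inflated whatever SMA does, that the stated power is lost, or that Table 2 needs changing. This is an inexpensive improvement worth making, not a defect that undermines the trial.

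**What to change.** 1. Record the SMA group, or the session if groups roll, for every SMA patient, and state whether groups are closed or rolling.
2. In the Aim 1 models (KCCQ and EQ5D) and the Aim 3 models, add a post-baseline group effect in the SMA arm only: a random group-by-time effect, or a group random slope that is zero at baseline. Treat usual-care patients and non-attenders as singletons, and use Satterthwaite or Kenward-Roger degrees of freedom. If groups roll, use a multiple-membership version.
3. Do not rely on a group random intercept that is constant over time, because it cancels from the treatment-by-time contrast.
4. For Aim 2, report group-robust standard errors as a sensitivity analysis. If groups roll, define one cluster per patient in advance, such as the group at the first session attended.

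The cost is one data field, one extra variance term (a more complex model if groups roll) and slightly wider intervals. If the group variance proves close to zero, the results will barely change.
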